4.4 Treatment Assignment Procedures

4.4.1 Randomization Procedures

Participants will be randomized at the participant level to one of three arms: 1) BLTR with target incision height of 3 mm 2) BLTR with target incision height of 5 mm and 3) Trabut with target incision height of 3 mm. Both eyes will be operated with the same surgical procedure and incision height if both eyes need surgery. Randomization assignments will be prepared in individual opaque envelopes with the patient ID number on both the outside of the envelope and on the internal papers indicating the arm assigned. The envelope will be opened during enrollment by the Program Manager. The surgeon and surgical assistant will both confirm the assigned surgical procedure and incision height at the start of the procedure. They will be required to indicate the assigned procedure and height on the surgical evaluation form and to measure and record the actual height of the incision made. Incision heights will be measured for patients in all three randomization arms.

The randomization assignments will be developed at UNC. Each week reported assigned surgical procedures and incision heights will be compared against the master table to ensure the assigned procedure and heights are consistently being reported for each participant. Details on monitoring are available in the quality assurance section.

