6 STUDY SCHEDULE

Visit Type	Timing	Window
Eligibility Screening	Day 0	N/a (potential subjects to be screened for eligibility when they present for surgery)
Enrollment and Baseline Exam	Day 0	N/a (subjects to be enrolled right after screening)
Surgery	Day 0	0-14 days after enrollment. If surgery must be delayed more than 2 weeks, a new baseline exam should be completed.
1-day post-operative visit	Day 1	Day 1-2
Suture Removal	2 weeks after surgery	10 – 18 days after surgery
6 week follow up	6 weeks after surgery	5 to 9 weeks post-surgery
12 month follow up	12 months after surgery	11 to 18 months post-surgery
3 year follow up	3 years after surgery	30 to 42 months post-surgery

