6.1 Eligibility Screening and Enrollment (Day 0)

Eligibility screening will take place at trichiasis surgery camps. Prior to this, local eye care workers will have identified all individuals with trichiasis and scheduled them for surgery. When patients present for trichiasis surgery, a trichiasis surgeon or screener will screen them for the presence of trichiasis and will note whether prior surgery has been performed on any eye that has trichiasis that day. Then the consent specialists will make a general announcement about the study and invite those who would like to learn more and possibly participate to meet individually with one of them.

The consent specialists will meet with trichiasis surgery patients in small groups to tell them about the study and then individually will assess eligibility using the Eligibility Review form. If they are eligible and interested in participating, the consent specialist will proceed to obtain informed consent with one patient at a time. The full process for

obtaining informed consent is provided in the Manual of Procedures. Those who provide consent will then meet with the project manager to be enrolled in the study.

Required Procedures/Data Collection:

- Complete Eligibility Screening form (Form 1)
- Obtain informed consent
- Collect Demographic and Tracking Information

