6.2 Baseline Ocular Exam and Surgery (Day 0)

The baseline exam occurs immediately after enrollment and just prior to surgery (all happen on the same day). The goal of this exam is to characterize trichiasis severity and visual acuity prior to surgery. Baseline trichiasis severity is an important predictor of post-operative trichiasis; hence, these data will be included in all models evaluating the outcome.

After the ocular exam, the patient receives trichiasis surgery.

Required Data Collection:

- Baseline Ocular Exam Form
- Surgical Evaluation Form

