9.3 Analysis Plan

We will follow these general analysis principles:

- The primary analyses will be performed according to the participant's assigned intervention.
- All participants who complete randomization and have surgery performed will be included in analyses.
- All events following surgery will be counted.
- All analyses will be conducted at the eye level, using the generalized estimating equations approach to correct standard errors (to account for the correlation between two eyes of a subject).
- Unless otherwise indicated, three sets of analyses will be performed: 1) BLTR 3 mm versus BLTR 5 mm and 2) BLTR 3 mm versus Trabut 3 mm 3) BLTR 5 mm versus Trabut 3 mm.

Post-operative Trichiasis Analyses:

The primary analyses will be based on the dichotomous outcome: presence or absence of post-operative trichiasis at any time point within 12-18 months following surgery. Both unadjusted and adjusted analyses will be performed. Adjusted analyses will account for the severity of pre-operative trichiasis, with severity defined based on the table below.

Trichiasis Severity Classification	Description
Mild	1-4 Eyelashes touching globe, no epilation OR 1-10 Eyelashes epilated, no eyelashes touching globe

Moderate	5-9 Eyelashes touching globe, no epilation OR 1-4 Eyelashes touching globe and 1-10 eyelashes epilated
Severe	5-9 Eyelashes touching globe and 1-10 eyelashes epilated OR 10+ Eyelashes touching globe, regardless of epilation status OR 11-20 Eyelashes epilated, regardless of eyelashes touching globe OR Entire eyelid epilated

(Gower et al. 2013. *JAMA Ophthalmol.*;131(3):294-301.)

Multiple secondary analyses of post-operative trichiasis will be performed. We will compare the severity of post-operative trichiasis between groups, with severity defined using the table above. First, we will compare the primary groups utilizing severity at first observation (6 weeks or 12 months for the primary outcome). Then we will compare groups using severity at final observation. This will allow us to determine whether one group has a higher ‘surgical failure’ rate and whether recurrent trichiasis progression varies across interventions. We will conduct both unadjusted and adjusted analyses.

Eyelid Contour Abnormalities:

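### As written, the allocation envelope is opened before baseline severity is graded and before surgery, which leaves an avoidable opportunity for bias in the adjusted analysis and in the analysed set

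*Combined protocol and SAP*

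**What the plan says.** Five parts of the combined protocol and SAP bear on the order of events.

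- **Allocation (4.4.1):** "The envelope will be opened during enrollment by the Program Manager". Under 6.1, enrolment follows consent: "Those who provide consent will then meet with the project manager to be enrolled in the study". I take the Program Manager and the project manager to be the same role.
- **Baseline exam (6.2):** "The baseline exam occurs immediately after enrollment and just prior to surgery (all happen on the same day".
- **Schedule (6):** the window for surgery is "0-14 days after enrollment. If surgery must be delayed more than 2 weeks, a new baseline exam should be completed".
- **Use of severity (6.2 and 9.3):** "Baseline trichiasis severity is an important predictor of post-operative trichiasis; hence, these data will be included in all models evaluating the outcome", and "Adjusted analyses will account for the severity of pre-operative trichiasis, with severity defined based on the table below". Section 9.3 also states "Both unadjusted and adjusted analyses will be performed".
- **Analysed set (9.3):** "All participants who complete randomization and have surgery performed will be included in analyses".

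On masking, 4.4.2 covers the participant and the outcomes assessment team, and says that the surgeon cannot be masked. Section 5.1 gives the surgeon the assignment only shortly before operating. The baseline examiner is neither identified nor mentioned in the masking provisions.

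**The concern.** A baseline covariate protects a randomised comparison because it cannot depend on the arm. That is guaranteed only if it is recorded before the arm is revealed, or by someone who does not know it. Here neither condition is stated. The severity classes in 9.3 turn on counts of touching and epilated lashes, with cut-points between 4 and 5 and between 9 and 10 touching lashes, so a small difference in counting can move an eyelid by one class. If grading leaned with the arm, the adjusted comparison would correct for a difference that does not exist.

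The second issue is separate and would reach the unadjusted analysis too. Anyone randomised but not operated drops out of the analysis. If dropping out were related to both arm and risk, the groups compared would no longer be the groups randomised. The longer the gap between opening the envelope and surgery, the more room there is for this.

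**Working it through.** The point rests on sequence, and the plan gives no figure of its own to reproduce.

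**Sequence**

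1. Screening for trichiasis and prior surgery, then eligibility review and consent (6.1). These come before allocation, so participant eligibility is settled first.
2. Enrolment, with the envelope opened (4.4.1, 6.1).
3. Baseline exam, following enrolment (6.2).
4. The surgeon is told the arm (5.1).
5. Surgery, on the same day according to 6.2, or 0 to 14 days after enrolment according to the schedule in section 6. A longer delay brings a new baseline exam.

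So severity (step 3) and receipt of surgery (step 5) both come after step 2. Section 4.4.2 keeps the outcomes assessors away from the surgical site, so the baseline grader at the camp is apparently someone else, for whom no masking is stated. Sections 6 and 6.2 do not agree on timing.

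**Illustration 1: severity graded differently in one arm.** The inputs are assumptions. Suppose adjacent classes differ by 5 to 10 percentage points in recurrence, and 5% to 10% of eyelids in one arm are graded one class too high. To first order:

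shift in adjusted difference = share misgraded × gap between classes

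- Low end: 0.05 × 5 = 0.25 points.
- High end: 0.10 × 10 = 1.0 point.

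The target difference in 9.2 is 15% − 0.75 × 15% = 3.75 points. The shift is therefore 0.25/3.75 = 7% to 1.0/3.75 = 27% of the target, if the assumptions held.

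**Illustration 2: participants lost before surgery in one arm only.** From 9.2: 4,953 participants, three equal arms, 5% loss to follow-up, 40% bilateral, between-eye correlation 0.24, base rate 15%.

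- Participants per arm: 4,953/3 = 1,651.
- Eyes per arm after loss: 1,651 × 0.95 × 1.4 = about 2,196.
- Design effect: (0.6 + 0.4 × 2 × 1.24)/1.4 = 1.137.
- Effective eyes per arm: 2,196/1.137 = about 1,931, held fixed for simplicity.

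Suppose no true difference. One arm loses a share x before surgery, and those people would have had risk r. Both x and r are assumptions. The observed rate in that arm is (0.15 − x·r)/(1 − x).

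| x (people) | r | Rate in that arm | Apparent RR | Two-sided rejection rate at 5% |
|---|---|---|---|---|
| any | 15% | 15.0% | 1.00 | 5.0% |
| 2% (33) | 30% | 14.7% | 0.98 | 5.8% |
| 2% (33) | 45% | 14.4% | 0.96 | 8.4% |
| 5% (83) | 30% | 14.2% | 0.947 | 10.7% |
| 5% (83) | 45% | 13.4% | 0.895 | 29% |

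For example, with x = 0.05 and r = 0.30: (0.15 − 0.015)/0.95 = 0.142, and 0.142/0.15 = 0.947.

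**The case against.** The strongest reply is that very few people know the arm in time to act on it. Only the Program Manager is documented as knowing it before the surgeon is told, and participants are masked. That closes most routes to arm-related refusal or cancellation until the last moment. This stands, and it limits the concern to an opportunity.

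The order itself can be questioned. The schedule in section 6 lists enrolment and baseline exam as one Day 0 visit, so opening the envelope during enrolment might be meant to follow the exam. Section 7 refers to a Manual of Procedures, not among the documents reviewed, which may settle this. That is fair, but the protocol text points the other way and should be made explicit.

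Requiring surgery for inclusion is understandable, because post-operative trichiasis has no natural meaning for an unoperated eyelid. That also stands. It is a reason to keep the gap between allocation and surgery short, since analysis cannot readily recover these people.

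There are partial safeguards. An unadjusted analysis is planned, and misgraded severity cannot affect it. Preoperative photographs (section 7) may allow some audit of grading. However, the Précis describes the group comparisons as adjusted for severity, so the adjusted result is not a side analysis.

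A reader might infer that participants commonly wait two weeks with the arm known. The documents do not support this: 6.2 describes a same-day process, 4.3 recruits on the day of surgery, and the repeat exam applies only when the delay exceeds two weeks.

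**Conclusion.** The point holds as an avoidable weakness in the stated procedure. Allocation is revealed before severity is graded and before surgery, and nothing in the plan masks the baseline examiner or holds the assignment back.

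Two stronger readings are tempting and are not supported. One is that the baseline examiner knew the arm and that the severity grades are therefore biased; no section says the examiner sees the assignment. The other is that the analysed set destroys the randomised comparison. Exclusions matter only if they differ by arm and relate to risk, and the documents give neither the number of unoperated participants nor a reason to expect such a pattern.

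The size of any bias cannot be derived from the documents. The illustrations run from no effect to an apparent relative risk of 0.895, and the extreme needs 5% lost from one arm only, at three times the base risk. The case for change rests on its low cost rather than on demonstrated harm.

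**What to change.** In 4.4.1 and 6.1–6.2, state that the envelope is opened only after the Baseline Ocular Exam Form is complete and the participant is ready for surgery that day. This reorders two steps that 6.2 already places on the same day, fits the surgeon notification in 5.1, and needs no extra staff or procedure. State also who grades baseline severity and whether that person is masked.

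Reconcile the surgery window and repeat baseline exam in section 6 with the same-day description in 6.2. In 9.3, add a report by arm of baseline severity and of participants randomised but not operated.

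The timetable in 6.5 shows recruitment ending in March of the 2019–20 study year and records a Year 5 one-year follow-up that did not take place, so enrolment may already be complete. If so, the order can no longer be changed. The sponsor should then document the order actually used and whether the baseline grader knew the arm, give the by-arm counts, and present the unadjusted result alongside the adjusted one. These steps cost only a few lines of text and one table.

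Reordering largely removes the problem for future enrolment, though not entirely: a participant can still go unoperated after the envelope is opened.

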4.4.2 Masking Procedures

The study subject and the outcomes assessment team will be masked to treatment assignment. However, the surgeon will not be masked to the treatment assignment since s/he must know what procedure to perform and what height to make the incision at. In order to ensure the outcomes assessors remain masked, they will not be present at the surgical site, and they will not have access to data from the baseline and surgical visit.

4.5 Subject Withdrawal

Subjects may withdraw voluntarily from the study at any time. Because the intervention is a one-time intervention, the investigators should not have reason to withdraw a study subject for non-compliance.

5 STUDY INTERVENTION

In this trial, all subjects will receive trichiasis surgery using the BLTR or Trabut procedure. The primary study intervention is surgical procedure, with either Trabut or BLTR with 3 mm or 5 mm from the eyelid margin.

5.1 Study Procedural Intervention Description

Surgeons will receive the surgical procedure and incision height assignment just prior to surgery for that participant. Immediately before beginning surgery, the surgeon will confirm with the surgical assistant what the procedure is (BLTR or Trabut) and if BLTR, what the assigned target incision height is.

5.2 Procedures for Training of Clinicians on Procedural Intervention

Prior to recruitment, each study surgeon must be certified using the World Health Organization's checklist for final assessment of surgeons by an external evaluator ([name] [name], [name] or [name]) to ensure s/he consistently performs high-quality surgery following the World Health Organization's recommended procedure. Then the surgeon will be trained by the study oculoplastic surgeon, [name], on how to appropriately indicate where to make the incision and then to measure the incision after making it.

Target incision heights will be indicated using a sterile surgical marker. Each study surgeon will receive extensive practice in measuring the distance from the eyelid margin with calipers and marking the location of the incision across the length of the eyelid. We will utilize our surgical simulation device, HEAD START, to practice measuring and marking the incision height. Once surgeons are comfortable with the approach, we will prepare a series of incised eyelids (on HEAD START) and will ask the surgeons to measure the height of each incision nasally, centrally, and temporally. Once they reach a kappa of >0.7 for measuring the heights compared to [name] measurements, we will proceed to similar practice with live patients. Again, kappas of >0.7 for measuring the height of the incision will be required before the surgeon is able to work independently.

Monthly throughout the enrollment and surgery phase of the trial, one of the study ophthalmologists ([name], [name] and [name]) will visit the surgery team and will assess surgical measurements.

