5.3 Assessment of Clinician and/or Subject Compliance with Study Procedural Intervention

The Project Director will regularly monitor surgical activities in-person to ensure that the surgeons are following the study procedures, performing the correct procedure, and accurately measuring and recording the incision height. Each week the Coordinating Center (CC) will compare the assignment reported on the Surgical Evaluation form against the actual assignment. The CC will issue a query for each instance where there is any disagreement between the recorded assignment and actual assignment. The CC will also compare the reported assigned height on the Surgical Evaluation against the actual height measurements. Frequency of differences greater than 0.5mm will be reported at the surgeon level on a cumulative basis. Whenever more than 5% of the actual measurements are more than 0.5 mm different than the assigned measurements, the surgeon will be reevaluated by one of the study ophthalmologists to determine what corrective measures need to be made.

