Primary analyses of eyelid contour abnormalities will be based on a dichotomous variable: presence or absence of moderate/severe contour abnormality at the last study visit where the participant was seen between 6 weeks and 12-18 months, , or at last visit before repeat surgery using the photograph grade, which will be based on the definitions below. For the purposes of this analysis, mild will be combined with “no abnormality” and moderate and severe will be combined to form the “moderate/severe contour abnormality” group.

Abnormality	Definition
Mild	Vertical deviation from the natural contour, 1 mm in height (less than half the pupil height in daylight) and affecting 1/3 of horizontal eyelid length
Moderate	Vertical deviation from the natural contour 1–2 mm in height (about the pupil height in daylight) or affecting 1/3–2/3 of horizontal eyelid length
Severe	Vertical deviation from the natural contour 2 mm in height (more than the pupil height in daylight) or a defect >2/3 of the horizontal eyelid length

(Gower et al. 2012 *PLoS Negl Trop Dis* 6(6): e1713)

Secondary analyses will explore the relationship between incision height and the full range of eyelid contour abnormalities, which will require use of the photographic grade that will be graded centrally.

Targeted versus Actual Incision Height:

We will conduct an analysis to compare the assigned incision height against the actual incision height measured during surgery. If more than 10% of the heights vary by more than 0.5 mm, we will conduct secondary analyses for each of the above analyses to determine whether the results of the actual incision height analyses are similar to the per-protocol analyses. If differences exist, we will report these analyses separately, but will emphasize that the per-protocol analyses are the primary analyses.

New Versus Conversion Surgeons

Analyses will also be conducted stratifying based on surgeons' prior experience. Specifically, we will conduct all above analyses based on whether surgeons were trained on both bilamellar and Trabut simultaneously, or whether they first learned bilamellar and received additional training in Trabut at a later time.

1-day Surgical Corrections

Finally, we will conduct an analysis to determine whether there is a difference in the rate of 1-day surgical corrections by study arm.

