10.1 Training

All personnel will undergo extensive training to ensure consistency in data-collection procedures. We will begin with an ethics training session for all study staff, and ethics certification will be required from each staff member before the study begins. We will then provide an overview of the study design, each team member's responsibilities, and how members integrate to form a cohesive data-collection team. Then, a two-day training session will be held for each data-collection group to ensure they understand forms completion and the details of the data that they are supposed to collect.

The recruitment team, surgical assistants, and study coordinators will be trained on appropriate methods for conducting in-person interviews and use of the data-collection forms. Training for all personnel will include didactic instruction and clinical demonstration with live subjects. Upon completion of training, all personnel will be evaluated for all procedures that they will be asked to perform. Only those who pass certification will continue with the study team.

An independent evaluator will critically examine all surgeons to ensure that they perform high-quality surgery and follow recommended WHO procedures. Each surgeon will be evaluated using the WHO certification checklist and only certified surgeons will be allowed to participate in the study. [name] will train the surgeons on how to consistently measure incision heights and incision lengths. We will require $\kappa > 0.7$ for each measurement comparing the individual surgeon to [name] before the surgeon will be considered proficient in collecting these measures.

The outcomes examiner will be trained on how to grade trichiasis and eyelid contour abnormalities using photographs and actual trichiasis patients. κ of 0.7 will be required before the examiner is certified. In the second year of the trial, recertification for all patient examiners will be held at the start of the second series of surgical camps and 12-month follow ups.

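### Certifying incision-height measurement by an unspecified kappa above 0.7 does not show that a surgeon measures within the trial's own 0.5 mm tolerance

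*Combined protocol and SAP*

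**What the plan says.** Section 5.2 has surgeons use calipers to find and mark the incision line. For certification, the trainers prepare incised lids on the HEAD START simulator and "ask the surgeons to measure the height of each incision nasally, centrally, and temporally". A kappa above 0.7 against the reference measurer is needed there, and then again on live patients: "kappas of >0.7 for measuring the height of the incision will be required before the surgeon is able to work independently". Section 10.1 restates the threshold for incision heights and lengths, to be met "before the surgeon will be considered proficient in collecting these measures". Neither section states the categories, the weights, the number or spread of test lids, a check for bias, or a limit in mm.

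Delivery of the intervention is judged in mm. Under section 5.3, "Frequency of differences greater than 0.5mm will be reported at the surgeon level on a cumulative basis", and the trigger for re-evaluating a surgeon is: "Whenever more than 5% of the actual measurements are more than 0.5 mm different than the assigned measurements". Section 9.3 adds: "If more than 10% of the heights vary by more than 0.5 mm, we will conduct secondary analyses". By section 4.4.1, the height used in these checks is the one that the operating team measures and records, in all three arms.

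**The concern.** Kappa measures chance-corrected agreement between categories. Applied to a continuous reading, its value depends on where the bins fall, how disagreements are weighted and how widely the test heights are spread. It is not expressed in mm and does not separate a constant offset from random scatter. The protocol fixes none of these choices, so a pass cannot be translated into a statement about 0.5 mm.

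The two BLTR targets are 2 mm apart. The surgeon measures once to mark the target and again to record the cut. An offset that affects both steps would move the incision and also hide the move: the recorded height would agree with the assignment, and neither the 5% nor the 10% trigger would respond. Certification is the only step with a numeric standard for how accurately the team measures.

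**Working it through.** The documents derive neither the 0.7 nor the 0.5 mm, so there is no plan figure to reproduce. The check asks whether one fixed error in mm gets the same pass or fail under different reasonable kappas.

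**Inputs from the documents:** pass mark kappa > 0.7 (5.2, 10.1); tolerance 0.5 mm with a 5% trigger (5.3) and a 10% trigger (9.3); BLTR targets 3 and 5 mm (4.4.1).

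**Assumed, because the documents do not say:** reference heights are either half near 3 mm and half near 5 mm (SD 0.3 mm each) or uniform over 2 to 6 mm; surgeon reading = reference + bias + normal error; a single cut at 4 mm, or 1 mm or 0.5 mm bins; unweighted, linear or quadratic weights. The kappas come from simulations of 200,000 to 400,000 paired readings.

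**Two measurers, in mm:**
- A: bias 0.75 mm, SD 0.1 mm. Share beyond 0.5 mm = Φ((0.75 − 0.5)/0.1) = Φ(2.5) ≈ 99%.
- B: no bias, SD 0.25 mm. Share beyond 0.5 mm = 2 × (1 − Φ(0.5/0.25)) = 2 × (1 − Φ(2)) ≈ 4.5%, inside the 5% trigger.

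**Kappa for each (lids near 3 and 5 mm / uniform 2 to 6 mm):**

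| Kappa | A: 99% beyond 0.5 mm | B: 4.5% beyond 0.5 mm |
|---|---|---|
| 3 versus 5, cut at 4 mm | 0.79 / 0.62 | 0.99 / 0.90 |
| Quadratic weights, 1 mm bins | 0.73 / 0.79 | above 0.9 / above 0.9 |
| Quadratic weights, 0.5 mm bins | 0.78 / 0.81 | above 0.9 / above 0.9 |
| Linear weights, 1 or 0.5 mm bins | 0.43 to 0.50 | above 0.8 / above 0.8 |
| Unweighted, 1 mm bins | below 0.1 | 0.74 / about 0.75 |
| Unweighted, 0.5 mm bins | below 0 | 0.52 / 0.56 |

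**Hand check of the 0.79.** For lids near 3 mm, A's readings have mean 3.75 and SD √(0.3² + 0.1²) = 0.316. The chance of reading above 4 is 1 − Φ(0.25/0.316) ≈ 0.215. Lids near 5 mm are almost never misclassified. Disagreement ≈ 0.5 × 0.215 = 0.107, so observed agreement ≈ 0.893. The reference splits 50:50, so chance agreement is 0.5. Kappa ≈ (0.893 − 0.5)/(1 − 0.5) ≈ 0.79.

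**Reading the table.** A passes in the quadratic rows and, with lids near the two targets, on the 3-versus-5 cut; A fails everywhere else. B passes everywhere except on unweighted 0.5 mm bins. The spread of test heights matters too: if all lids are near 3 mm (SD 0.3 mm), B scores only 0.37 on unweighted 0.5 mm bins.

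**What a mm rule implies.** With no bias, at most 5% of readings beyond 0.5 mm requires SD ≤ 0.5/1.96 = 0.255 mm. At most 10% requires SD ≤ 0.5/1.645 = 0.304 mm.

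**The case against.** A reader might infer that kappa is lenient and will let poor measurers through. The documents do not support that. Some kappas are stricter than the tolerance: unweighted 0.5 mm bins reject even measurer B. The lenient results for A depend on a two-way cut or quadratic weights, neither of which the protocol mentions, and the two-way cut rejects A when heights are uniform. The Manual of Procedures, which section 7 cites for how to measure and mark, was not available and may define the categories. What stands is that the protocol's rule has no determinate meaning in mm. Naming the categories would settle which kappa applies, but would still not report bias.

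The 0.5 mm rule also concerns placement (assigned against actual height), whereas kappa certifies measurement. That is correct, and the shares computed above are measurement errors, not forecasts of how often the section 5.3 trigger fires. The two are linked because the placement check relies on the team's own readings.

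Kappa is not the only safeguard. Study ophthalmologists visit monthly to assess measurements and correct drift (5.2, 10.2), the Project Director monitors measuring and recording in person (5.3), and lids are photographed after the incision (section 7). Any of these could expose an offset, but none states a criterion in mm.

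A reader might also infer that the primary result is compromised. It is not: section 9.3 analyses by assigned intervention, and measurement error changes neither the arm labels nor the trichiasis outcome. A constant offset would move both BLTR targets equally and leave them 2 mm apart.

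**Conclusion.** The concern holds in limited form. The certification standard is not in the unit the trial uses to judge delivery, and passing it does not demonstrate measurement within 0.5 mm. Depending on unstated choices, a surgeon with 99% of readings outside the tolerance could pass and one with 4.5% outside could fail. These figures rest on the assumed height and error distributions. They show that the result turns on an unstated choice, not how often surgeons would be misjudged. The consequence is confined to the fidelity monitoring in 5.3 and the conditional actual-height secondary analyses in 9.3; no effect on power or bias for the primary outcome has been shown. Severity is minor, and the change is a cheap improvement.

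**What to change.** In sections 5.2 and 10.1, replace kappa for incision height with agreement in mm, computed from the same paired certification readings. Report the mean difference and limits of agreement against the reference measurer, and require at least 95% of readings within 0.5 mm, which matches the 5% trigger in 5.3. State the number of test lids, and include incisions near both 3 and 5 mm, on HEAD START at least. Live lids near 5 mm may be scarce before the trial, because section 2.1 gives 3 mm as the currently recommended height. Where paired readings are taken at the monthly visits, summarize them in the same way. Keep kappa for the categorical grades (post-operative trichiasis and contour abnormality).

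The cost is wording in two sections and in the Manual of Procedures, plus some 5 mm simulator lids if the set does not already include them. The certification readings are already planned, so only their summary changes. The downside is that some surgeons may need more practice before they are certified.
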